8.7.5 Handling of adverse reactions/events

AE: an unexpected medical event a subject experiences during the clinical trial, which is not necessarily caused by or related to the vaccine/vaccination.

AR: an unexpected or untoward reaction during the vaccination at the prescribed dose and according to prescribed procedures, which is usually related to vaccination.

Serious adverse event (SAE): an important medical event not necessarily caused by or related to clinical trials of vaccines, which leads to: 1) death; 2) life-threatening situation; 3) hospitalization or prolonged hospitalization; 4) permanent or significant disability/incapacity; 5) congenital anomaly or birth defect; or 6) other important medical events that may cause the conditions above without treatment.

Suspected unexpected serious adverse reaction (SUSAR): A suspected AR refers to an untoward and unintended reaction at any dose, analyzed to be at least possibly related to the drug; an unexpected AR refers to that the nature, severity, outcome, or frequency of the AR is inconsistent with the expected risks described in the protocol or other relevant information (e.g., the Investigator's Brochure and package insert).

Subjects should report any clinically significant diseases/events after vaccination to the investigator in a timely manner. The investigator should follow up the AR/AE until the symptoms disappear or become stable. Necessary treatment and management will be provided unconditionally when deemed necessary by the investigator in order to relieve the subject from suffering from the AR/AE. All medications and medical management will be recorded during each follow-up.

If a SAE/SAR occurs, the investigator should take necessary measures immediately, complete the "Serious Adverse Event Report Form", and report it to the PI and the study center via fax or email within 24 h.

8.7.6 Reporting procedures for serious adverse events

In case of any SAE, whether or not related to the investigational vaccines, the investigator must complete the "Serious Adverse Event Reporting Form" after being informed and report it to the PI and the vaccine manufacturer via fax or email within 24 h. The report should include a description, onset, type, duration, causality with vaccination, outcome, and treatment (symptomatic treatment) of the AE.

Upon receipt of a SAE report, the study center should confer with the investigator to determine if the subject should continue or discontinue trial participation in consideration of the duration, range, intensity, and outcome of the AE, as well as the subject's will. The study center should determine if the SAE is a SUSAR; if so, the study center should report it to the Center for Drug Evaluation, NMPA and the PI, and the PI should report the SUSAR to the Institutional Review Board.

For SUSARs which are fatal or life-threatening, the study center should, after the first knowledge, report them to the Center for Drug Evaluation, NMPA as soon as possible (not more than 7 natural days), report within the following 8 days and complete the follow-up information.

For SUSARs which are not fatal or life-threatening or other potentially serious safety risk information, the study center should, after the first knowledge, report to the Center for Drug Evaluation, NMPA (not more than 15 natural days). The investigator should record SAEs truthfully and evaluate and discuss them in the final report after trial completion or termination.

Table 8.7-4. Contact information of the Institutional Review Board

Institutional Review Board of Jiangsu Provincial Center for Disease Control and Prevention	Contact: [name] [contact]	E-mail: [contact]
--	--------------------------------------	---------------------

8.7.7 Handling of pregnancy events

Subjects are not allowed to participate in the investigational vaccine immunization during pregnancy. Urine pregnancy tests will be performed on subjects before vaccination and those tested positive will not be enrolled. If a pregnancy event is collected within 6 months of follow-up visits, a "Pregnancy Event Reporting Form" should be completed.

8.8 Immunogenicity Evaluation

8.8.1 Sample collection

For the immunogenicity group, 10.0 mL of venous blood will be collected on day 0 (V1), day 14 (V2, time window of ± 3 days), day 28 (V3, time window of ± 5 days), month 3 (V4, time window of ± 15 days), and month 6 (V5, time window of ± 15 days) after vaccination, and 2.0 mL of saliva will be collected on day 0 (V1), day 14 (V2), day 28 (V3, time window of ± 5 days), month 3 (V4, time window of ± 15 days), and month 6 (V5, time window of ± 15 days) after vaccination. For subjects in the cellular immunity group, 15.0 mL of venous blood will be collected on day 0 (V1) and day 14 (V2, time window of ± 3 days) after vaccination.

Vacuum blood collection tubes containing serum separator gels are used. Sample refrigeration prior to centrifugation is not allowed in order to minimize the risk of hemolysis and to avoid blood cell contamination during serum transfer to the target serum tube. Serum is separated on the blood collection day and stored at $-20\text{ }^{\circ}\text{C}$ or below for serum antibody testing and backup.

According to the operating manual, the saliva samples will be stored at -20°C or below and delivered to the testing laboratory in time.

Cellular immunity samples will be collected in vacuum blood collection tubes with anticoagulant. PBMC will be separated and used for ICS on the day of blood collection.

The serum and saliva samples collected in this clinical trial will be used to evaluate the immune response of the investigational vaccine. Approval by the Institutional Review Board and consent of the subjects are required if used for other research purposes. Except for serum and saliva samples that are sent for testing, remaining backup samples will be transferred to a third-party laboratory at the end of the clinical trial. Blood and saliva samples may not be delivered abroad.

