Subjects assigned to receive an ICV booster dose will receive the vaccine from the same manufacturer as the two-dose prime immunization. All subjects will be issued diary cards on the day of vaccination and on Day 14 after vaccination for systematic safety observations. Venous blood and saliva samples will be collected from subjects in the immunogenicity group on the day of vaccination as well as 14 days, 28 days, 3 months, and 6 months after vaccination to test for serum antibody titers, serum IgA, and SIgA. Venous blood samples will be collected from subjects in the cellular immunity group on the day of vaccination and 14 days after vaccination to test for cellular immunity. All subjects are required to complete interviews on the day of vaccination as well as 14 and 28 days after vaccination. Subjects in the immunogenicity group are also required to complete 3- and 6-month follow-up visits. The remaining subjects may complete the 3- and 6-month visits via telephone follow-up. When about 2000 subjects (first stage) and 5000 subjects (second stage) are enrolled, the safety of all subjects in the early stage should be evaluated, and the enrollment schedule should be continued with the consent of PI. Enrollment will be suspended

or terminated immediately if a safety issue with vaccination is found to meet the suspension or termination criteria.

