6.1 Study Endpoints

6.1.1 Primary endpoints

- 1) Incidence of ARs within 0–28 days after booster immunization.
- 2) Geometric mean titer (GMT) of anti-SARS-CoV-2 specific neutralizing antibodies against omicron BA.4/5 in subjects in the immunogenicity group at 28 days after booster immunization.

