6.1.2 Secondary endpoints

Immunogenicity endpoints:

- 1) Seroconversion rate and geometric mean increase (GMI) of anti-SARS-CoV-2 neutralizing antibodies in subjects in the immunogenicity group at 28 days after immunization;
- 2) Seroconversion rate, GMT, and GMI of anti-SARS-CoV-2 neutralizing antibodies in subjects in the immunogenicity group at 14 days, 3 months, and 6 months after booster immunization;
- 3) Geometric mean concentration (GMC), seroconversion rate, and GMI of anti-SARS-CoV-2 RBD protein IgG antibodies in subjects in the immunogenicity group at 14 days, 28 days, 3 months, and 6 months after booster immunization.

Safety endpoints:

- 1) Incidence of adverse reactions within 30 minutes after booster immunization;
- 2) Incidence of adverse reactions within 0–14 days after booster immunization;
- 3) Incidence of adverse events within 0–28 days after booster immunization;
- 4) Incidence of serious adverse events (SAEs) within 6 months after booster immunization.

Exploratory endpoints:

- 1) Baseline anti-Ad5 vector neutralizing antibody titer in subjects in the immunogenicity group, and stratified analysis based on baseline anti-Ad5 vector neutralizing antibody titer ($> 1:200$, $\leq 1:200$);
- 2) GMT, seroconversion rate, and GMI of certain VOC/VOI cross-neutralizing antibodies in subjects in the immunogenicity group at 28 days after booster immunization;

- 3) GMC, seroconversion rate, and GMI of salivary IgA and serum IgA antibodies in subjects in the immunogenicity group at 14 days, 28 days, 3 months, and 6 months after booster immunization;
- 4) Seropositive rate and response levels of IFN- γ , TNF- α , IL-2, IL-4, IL-5, and IL-13 in CD4⁺ and CD8⁺ stimulated by S protein overlapping peptide library using ICS in subjects in the cellular immunization group at 14 days after booster immunization.

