8.7 Safety Follow-Up and Evaluation

8.7.1 Safety observation

All subjects will remain on site for a 30-min observation period after receiving the vaccination. Investigators will observe each and every one of the subjects and record both regional and systemic responses reported during the 30-min observation period, as well as their severity.

A safety follow-up will be performed within 14 days after vaccination for all subjects, during which the investigator will systematically examine each subject for ARs, and the subject will fill in the "Vaccination Diary Card (Within 14 Days)" according to their symptoms and signs. From day 15 to day 28 after vaccination, post-vaccination AEs should be observed through spontaneous reporting and regular follow-ups. The investigators will inquire and check the diary cards at the next visit and guide the subjects in completing the cards. From day 28 to month 6 after vaccination, safety follow-ups on SAEs should be performed by spontaneous reporting.

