8.9 On-Site Workflow

8.9.1 Overview of visit procedures

From the beginning of the screening prior to the enrollment to the end of the study, the subjects will complete all the study content in 5 or 6 visits. The specific time, time window, and content for each visit are detailed in 8.9-1.

Table 8.9-1. Visit procedures

Visit point	V1	V2	V3	V4	V5
Visit time	D-7-D0	D14	D28	Month 3	Month 6
Time window	/	± 3 days	± 5 days	± 15 days	± 15 days
Informed consent	•				
Registration/identity verification	•	•	•	•	•
Physical examination (blood pressure, height, weight, body temperature)	•				
Urine pregnancy (female of childbearing potential)	•				
Medical history inquiry and eligibility screening	•				
Randomization number assignment ^a	•				
Immunogenicity blood sampling ^a	10 mL	10 mL	10 mL	10 mL	10 mL
Cellular immunity blood sampling ^b	15 mL	15 mL			
Saliva sampling ^c	2 mL	2 mL	2 mL	2 mL	2 mL
Immunization ^d	•				
Dispensation of diary card (0–14 days)	•				
Return of diary card (0–14 days)		•			
Dispensation of diary card (after 14 days)					
Return of diary card (after 14 days)			•		
Safety observations ^e	•	•	•		
SAE observation and reporting ^f	•	•	•	•	•

- Immunogenicity group only;
- Subjects in the immunogenicity group recruited from Jiangsu CDC who are included in cellular immunity group only;
- Immunogenicity group only;
- If the investigator believes the health status of the subject on the day of vaccination is temporarily unsuitable for vaccination, the dose may be delayed up to 1 week;
- All adverse events within 0–28 days after immunization should be observed and documented, regardless of whether related to the vaccine;
- The investigator should fill out the "Serious Adverse Event Report Form" and complete the initial report within 24 h of learning of an SAE and complete the final report at the end of the event. Except for subjects in the immunogenicity subgroup, all subjects should complete V4–V5 via telephone

Table 8.9-2. Sample collection schedule at clinical trial visits

Visit	V1	V2	V3	V4	V5
Visit time	D0	D14	D28	Month 3	Month 6
Immunogenicity [#]	10 mL	10 mL	10 mL	10 mL	10 mL
Saliva [#]	2 mL	2 mL	2 mL	2 mL	2 mL
Cellular immunity [@]	15 mL	15 mL			

Note: # Immunogenicity group only

@ Subjects in the Jiangsu CDC who are included in cellular immunity group only

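### V3 may take back the diary on day 23 of a 0–28 day primary safety window, and the protocol gives conflicting methods for collecting SAEs from day 28 to month 6

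*Protocol*

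**What the plan says.** **Endpoints.** The first primary endpoint is "Incidence of ARs within 0–28 days after booster immunization" (Section 6.1.1). Section 6.1.2 adds all adverse events over the same 0–28 days and "Incidence of serious adverse events (SAEs) within 6 months after booster immunization".

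**Visit windows.** Section 8.8.1 gives "day 14 (V2, time window of ± 3 days), day 28 (V3, time window of ± 5 days" and, later, "month 3 (V4, time window of ± 15 days), and month 6 (V5, time window of ± 15 days". That section concerns blood and saliva in the immunogenicity group. Table 8.9-1 gives the same windows in the general visit schedule, which covers all subjects.

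**Diary and observation.** In the synopsis visit schedule and Table 8.9-1, the diary card for the period after day 14 is returned at V3. Table 8.9-1 marks safety observations at V1 to V3 only, and SAE observation at V1 to V5. Its note e asks for every adverse event of days 0–28 to be observed and documented. Section 8.7.1 adds, for days 15–28, spontaneous reporting together with regular follow-ups.

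**SAEs after day 28.** There are three wordings:

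- Section 8.7.1: "From day 28 to month 6 after vaccination, safety follow-ups on SAEs should be performed by spontaneous reporting".
- Section 6 (and the synopsis): "The remaining subjects may complete the 3- and 6-month visits via telephone follow-up".
- Note f to the visit table in Section 8.9.1 (and the synopsis): "Except for subjects in the immunogenicity subgroup, all subjects should complete V4–V5 via telephone".

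**The concern.** An incidence over a fixed window assumes that each subject in the denominator was asked about the whole window. Here the last scheduled adverse-event contact can fall inside the window. A site that follows the visit table exactly can collect the diary on day 23 and have no further dated contact until V4. Events starting on days 24–28 then depend on the subject volunteering them, while the subject still counts fully in the denominator.

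The 6-month SAE endpoint has a different problem: the text does not settle whether collection is passive or active. A site relying on Section 8.7.1 could make no calls; a site relying on note f would call everyone. At stake is the completeness of a primary and two secondary safety endpoints in about 10,000 subjects, in a trial whose safety sample size is justified by the chance of seeing a rare reaction at all.

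**Working it through.** **1. The V3 window against the 28-day endpoints.** Inputs: V3 at day 28 ± 5 (Table 8.9-1) and an endpoint window ending on day 28 (Sections 6.1.1 and 6.1.2).

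- Earliest compliant V3: 28 − 5 = day 23.
- Days left after the diary is returned: days 24 to 28, that is 5 days.
- Share of the window: 5/28 = 17.9%.
- Next scheduled contact: V4 at month 3 ± 15 days. With 30-day months (assumed), its latest date is 90 + 15 = day 105, so the longest in-window gap from V3 is 105 − 23 = 82 days.

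**2. What this could do to the stated detection probability.** Section 6.2 claims at least 85% power to see one case at an incidence of 0.02% in 10,000 subjects.

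- Reproduced: 1 − (1 − 0.0002)^10000 = 86.5%. The claim holds, with little margin.
- Capture needed to stay at 85%: (1 − 0.15^(1/10000)) / 0.0002 = 0.948. The figure drops below 85% once more than about 5% of such reactions are missed.
- Illustration, assuming onset uniform over 28 days and nothing captured after V3. With a fraction q of subjects seen on day 23, the captured rate is 0.0002 × (1 − q × 5/28):

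| q | Chance of at least one case |
|---|---|
| 0 | 86.5% |
| 10% | 86.0% |
| 25% | 85.2% |
| 50% | 83.8% |
| 100% | 80.7% |

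The document gives no distribution of visit days, so q is unknown. Uniform onset is pessimistic for reactions: Section 3.4.1 reports that most reactions in the earlier phase II trial fell in days 0–7 after each dose. It is less clearly pessimistic for adverse events of any cause.

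**3. The V5 window against the 6-month SAE endpoint.** With 30-day months, the earliest V5 is 180 − 15 = day 165. That leaves up to 15/180 = 8.3% of the window after the last scheduled query.

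**4. The SAE method, side by side.** Section 8.7.1 names only spontaneous reporting. Note f calls for telephone completion of V4 and V5, and Table 8.9-1 marks SAE observation at both visits. Section 6 uses *may*, immediately after saying that immunogenicity subjects are required to complete these visits. The first cannot be squared with the second as written; the third can be read either way.

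**5. Who is affected.** All ICV recipients are in the randomized group of 420, which attends V4 and V5 in person. Of the Ad5-nCoV-IH recipients, 10,000 of 10,000 + 210 (98%) are in the safety group. Section 8.11.4.2.4 plans a chi-square or Fisher comparison of 6-month SAEs between groups without saying which subjects enter it.

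**The case against.** The strongest reply is that the protocol does require observation to day 28. Note e sets that duty whatever the visit day, Section 8.7.1 mentions regular follow-ups for days 15–28, and Section 8.7.5 asks subjects to report clinically significant events promptly. The synopsis lists adverse-event observation at V4 and V5, and Table 8.9-4 assigns routine safety follow-up to V1 through V5. This stands to the extent that one cannot say the days after an early V3 go unobserved, only that they need not be observed. None of these passages fixes a contact on or shortly after day 28, and the synopsis disagrees with Table 8.9-1, which stops safety observations at V3.

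On SAEs, *may* in Section 6 can mean a choice of telephone over attendance rather than an optional contact, and the visits are already in the table. That narrows the conflict, but Section 8.7.1 still differs from note f.

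Some stronger readings are tempting but not supported:

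- **An early V2 loses days 12–14 of "Incidence of adverse reactions within 0–14 days after booster immunization".** It does not follow. The synopsis has the second card handed out at V2, and V3 is a further adverse-event contact for every subject.
- **The V3 window affects SAEs.** It does not. SAE observation is marked at all five visits.
- **The randomized comparison is biased.** Both randomized arms follow the same in-person schedule. Differential capture matters only if safety-group subjects are pooled into the between-group SAE comparison.

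**Conclusion.** The point holds in a limited form. A compliant V3 on day 23 leaves up to 5 of 28 days (18%) of the primary adverse-reaction window and the secondary adverse-event window without a scheduled contact, despite the stated duty to record to day 28. The likely effect on the adverse-reaction rate is small; it could be larger for 28-day adverse events. The detection probability of 86.5% would fall below 85% only if more than about 5% of the reactions of interest were missed. The 80.7% figure is an extreme that needs every V3 on day 23, uniform onset and no later capture.

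Separately, the SAE method from day 28 to month 6 is stated inconsistently, and V5 may close up to 15 days early. Passive capture could under-count 6-month SAEs in the safety group. This should be corrected, but it does not undermine the design.

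**What to change.** 1. Keep the ± windows for blood and saliva.
2. State in Section 8.7.1 and Table 8.9-1 that the second diary and the adverse-event query are completed on or after day 28, for example within 0 to +5 days, or by a short call to anyone seen earlier. Align the synopsis and the table on whether adverse events are observed at V4 and V5.
3. Reconcile Section 8.7.1, Section 6 (with the synopsis) and note f, so that the telephone SAE query already in the visit table is made for every safety-group subject at month 3 and on or after month 6. Spontaneous reporting can remain as an addition.
4. State in Section 8.11.4.2.4 whether the between-group SAE comparison is limited to the 420 randomized subjects.

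The cost is a minor amendment and brief calls to early attenders. Safety-group subjects give no samples at V3, so moving their window does not touch the assays, although it shortens the visit window from 11 days to 6. In the immunogenicity group, keeping the sampling window means at most 420 such calls.

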8.8.2 Assay of anti-SARS-CoV-2 specific neutralizing antibodies

The serum anti-SARS-CoV-2 S neutralizing antibody levels will be tested in subjects in the immunogenicity group before booster immunization as well as 14 days, 28 days, 3 months, and 6 months after immunization to compare the differences in antibody levels and persistence of the two vaccines.

8.8.3 ELISA assay of anti-SARS-CoV-2 RBD protein IgG antibodies

The serum anti-SARS-CoV-2 RBD protein IgG antibody levels will be tested in subjects in the immunogenicity group before booster immunization as well as 14 days, 28 days, 3 months, and 6 months after immunization to compare the differences in antibody levels and persistence of the two vaccines.

8.8.4 Assay of anti-recombinant replication-defective human adenovirus type 5 neutralizing antibodies

The serum anti-recombinant replication-defective human adenovirus type 5 neutralizing antibody levels will be tested in subjects in the immunogenicity group before booster immunization to determine the effects of baseline anti-Ad5 neutralizing antibody levels on anti-SARS-CoV-2 antibody levels.

8.8.5 Assay of salivary SIgA

The SIgA antibody levels will be tested in subjects in the immunogenicity group before booster immunization as well as 14 days, 28 days, 3 months, and 6 months after immunization to compare the difference in SIgA antibody levels between the two vaccines.

8.8.6 Assay of serum IgA

The serum IgA antibody levels will be tested in subjects in the immunogenicity group before booster immunization as well as 14 days, 28 days, 3 months, and 6 months after immunization to compare the difference in IgA antibody levels between the two vaccines.

8.8.7 VOC/VOI cross-neutralization testing

The levels of cross-neutralizing antibodies to VOC/COI will be tested in subjects in the immunogenicity group before and 28 days after booster immunization to compare the protective effects of the two vaccines on VOC and VOI.

8.8.8 Assay of antigen-specific CD4⁺ T cell and CD8⁺ T cell responses

The seropositive rates and response levels of IFN- γ , TNF- α , IL-2, IL-4, IL-5, and IL-13 in PBMCs will be tested in the subjected in the cellular immunity group before and 14 days after booster immunization to compare the difference in antibody levels between the two routes of administration.

Calculation of uncertain values: For antibodies determined by ELISA and neutralization assay, their GMT, GMI, and seroconversion rate will be calculated based on half of the respective starting value when a negative result is observed at the starting dilution and based on the maximum dilution when the maximum dilution is exceeded.

